11.5. Immunogenicity

Presence of anti-PF-00574659 antibodies will be listed and summarized by visit for each treatment group.

In subjects with a positive ADA, presence of neutralizing antibodies will be listed and summarized by visit for each treatment group.

These endpoints will be analyzed for the safety analysis set.

11.6. Physical Examination

Physical examination will be listed.

11.7. Enteric Pathogen

Enteric Pathogen data will be listed.

11.8. Other Safety Variables

11.8.1. Neurological Assessments

As part of the safety evaluation, the following neurological assessments are performed for each subject.

- Confrontational Visual Fields
- Timed 25-Foot Walk
- 9-Hole Peg Test (9-HPT)
- Symbol Digit Modality Test (SDMT)
- Patient-Multiple Sclerosis Neuropsychological Questionnaire (MSNQ)

To provide more precise results about the measurement, programming derived scores will be used in the listing and summary instead of the CRF recorded scores for SDMT. The derived standard deviation (SD) will be based on the age (derived based on test date and date of birth), education level (from the 1009 Social Status CRF page) and test score reported and the norm table provided in the protocol Appendix 7. When the test score is not equal to any of the norm scores, the closet norm score will be used to define the SD. When two norm scores have equal distance to the test score, the lower one will be used.

The neurological assessments will be summarized for the safety population by treatment group. In addition, a summary of clinically significant on-treatment changes in neurological assessments will be presented by treatment group, overall, and period. Clinically significant worsening changes are defined as the following:

- Symbol Digit Modality Test - 1 S.D. decrease or more on two consecutive visits, from the worst (smallest) case before first dosing;
- 9-hole Peg Test - 20% increase or more compared with the worst (greatest) case before first dosing;
- Confrontational Visual Fields Test - change from NORMAL to ABNORMAL when compared to the worst case before first dosing;
- 25-Foot Walk Test - 20% increase or more compared with the worst (greatest) case before first dosing.
- Patient-Multiple Sclerosis Neuropsychological Questionnaire - a 5-point increase or more compared with the worst (greatest) case before first dosing.

Neurological assessments will be listed. Separate listings for subjects with clinically significant on-treatment changes in neurological assessments will also be presented.

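### SDMT levels are rounded to the nearest norm score before a 1 SD cut-off is applied, so some falls below 1 SD count as clinically significant worsening

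*SAP*

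**What the plan says.** SAP Section 11.8.1 replaces the SDMT score entered on the case report form by a derived one, on the ground of precision: "To provide more precise results about the measurement, programming derived scores will be used". The derived quantity is an SD level looked up by age, education and test score in "the norm table provided in the protocol Appendix 7".

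Three rules fix the look-up and the criterion:

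- Age is not held at baseline: "The derived standard deviation (SD) will be based on the age (derived based on test date and date of birth), education level".
- A score that is not in the table takes the level of its nearest neighbour: "When the test score is not equal to any of the norm scores, the closet norm score will be used to define the SD". For ties: "When two norm scores have equal distance to the test score, the lower one will be used".
- Worsening is defined as: "Symbol Digit Modality Test - 1 S.D. decrease or more on two consecutive visits, from the worst (smallest) case before first dosing".

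The result feeds Table 14.3.6.14 (clinically significant on-treatment changes, by treatment group and period) and Listing 16.2.8.6.9.

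**The concern.** The criterion takes the difference between two rounded values and holds it against a sharp 1 SD limit. Each rounding can move a level by up to half a table step, so two scores less than 1 SD apart can land on levels exactly 1 SD apart. The derivation is justified by precision, yet it loses precision where the threshold is applied. Who appears in the table and listing then depends partly on the spacing of the norm scores and on where a subject's benchmark falls between them.

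Requiring two consecutive visits filters visit-to-visit noise. It does not filter this effect, because a score that settles at a lower value is rounded identically at both visits.

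A second question comes from taking age at each test date. If the norms are grouped in age bands, a birthday changes the look-up, and the SD level can move although the raw score has not.

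**Working it through.** The SAP gives no error rate for this criterion, so there is no figure to reproduce. The check applies the stated rule to assumed norm tables.

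**Inputs from the SAP.** Nearest norm score, ties down, age at test, threshold of 1 SD from the smallest pre-dose value (Section 11.8.1); treatment to Week 144 (Section 2.1).

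**Assumptions, because Appendix 7 is not shown.** Norm mean 55 points; SD 8, 10 or 12 points; table step 0.2, 0.25, 0.5 or 1 SD; norm scores in whole points. If scores and norms are whole numbers, the tie rule itself implies that some gaps are at least 2 points.

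**Example.** Take SD 10 and step 0.5 SD, so the norm scores are …45, 50, 55… with levels −1, −0.5, 0. A score of 53 is nearest to 55 (level 0). A score of 47 is nearest to 45 (level −1). The raw fall is 6 points, or 0.6 SD; the derived fall is 1 SD, and it is flagged.

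**Formula.** For a true fall *f* and step *s* (both in SD), write *f/s* = *n* + *r*, with *n* whole and 0 ≤ *r* < 1. If starting scores are spread evenly between norm scores, the rounded fall is *n* steps with probability 1 − *r* and *n* + 1 steps with probability *r*. A flag needs 1/*s* steps. For *f* = 0.75:

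- *s* = 0.2: 3.75 steps, 5 needed, flagged 0%.
- *s* = 0.25: 3 steps, 4 needed, flagged 0%.
- *s* = 0.5: 1.5 steps, 2 needed, flagged 50%.
- *s* = 1: 0.75 step, 1 needed, flagged 75%.

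**Whole-point check.** The rule was applied to every whole-number starting score within 2 SD of the mean, with the same norms at both visits and no measurement error:

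| Table step | Smallest fall that can be flagged | Flagged at about 0.75 SD | Flagged at 1 SD |
|---|---|---|---|
| 0.2–0.25 SD | 0.80–0.90 SD | 0–20% | 100% |
| 0.5 SD | 0.58–0.62 SD | 51–61% | 100% |
| 1 SD | 0.08–0.12 SD (1 point) | 76–80% | 100% |

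The 0.75 SD fall is taken to the nearest whole point: 6, 8 and 9 points for SD 8, 10 and 12. The upper ends come from SD 10, where 8 points is 0.80 SD. At exactly 0.75 SD the shares are 0%, 51–52% and 76%, in line with the formula.

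The 100% column holds because every step tried divides 1 SD evenly. With a step of 0.4 SD, for instance, a 1 SD fall is 2.5 steps and 3 are needed, so it would be flagged half the time. Below the lowest norm score, the nearest-score rule also stops registering further falls.

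**Age (conditional).** Week 144 is 144 × 7 / 365.25 = 2.76 years. With ages uniform within a band, the share of completers who change band is 2.76 divided by the band width: 55%, 28% and 14% for bands of 5, 10 and 20 years. Suppose the older band's mean is lower by 0.25, 0.5 or 0.75 SD. Among subjects who have crossed, a true 1 SD raw fall is then flagged for 0–80%, 0–52% and 0–29% of starting scores across the same grids. If norms rose with age, the shift would create flags instead.

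**The case against.** The strongest reply is that everything quantitative depends on a table that is not shown. With steps of 0.2–0.25 SD the distortion is small. Within the table and on evenly dividing grids, the error is towards flagging, which is the cautious direction for a safety screen. Age-at-test norms are ordinary age adjustment, and part of any shift is intended. The output is descriptive, with no hypothesis (SAP Section 2.5), and the same rule applies to both doses. All of this stands and limits the weight of the point. It does not remove the rounding, which follows from the text.

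Stronger conclusions are tempting but not supported:

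- **That the rule hides real cognitive decline.** With unchanged norms, no full 1 SD fall was missed in any grid tried. Masking at a change of age band needs a banded table with lower norms in the older band, and the SAP mentions neither bands nor direction.
- **That a definite share of stable subjects is falsely flagged.** With test error of 0.4 SD, 36 visits and two pre-dose tests, simulation gives 1.3% with exact scoring, 3.3% with 0.25 SD steps, about 8% with 0.5 SD steps and 27% with 1 SD steps. The SAP does not state the number of pre-dose tests; with four, the 0.5 SD figure is 1.6%.
- **That surveillance for PML depends on this listing.** The MSNQ also assesses cognition (Section 2.4 footnotes) and has its own raw-point criterion (Section 11.8.1). An external committee reviewed safety and adjudicated unexplained neurological findings (Section 14.2).

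**Conclusion.** The point holds for rounding. Section 11.8.1 applies a 1 SD limit to levels already rounded to the nearest norm score, so some falls below 1 SD are reported as clinically significant. How often depends on the spacing in Appendix 7: close to never at 0.75 SD if the table is fine, and for half to four fifths of starting scores if the step is 0.5 or 1 SD. The direction is over-flagging, provided that scores lie within the table, norms are unchanged and the step divides 1 SD evenly.

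The age point is secondary. It matters only if the table is banded, and then in either direction. About 28% of completers would change band by Week 144 under assumed 10-year bands.

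The consequence is confined to a descriptive safety table and listing for one of five neurological tests. It can change who appears there, which justifies a cheap correction but not a claim that the safety assessment is compromised.

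**What to change.** For the decline criterion in Section 11.8.1:

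1. Derive the SD level by linear interpolation between the two neighbouring norm scores. With norm scores *a* < *b* at levels *A* and *B*, a score *x* between them gets level *A* + (*x* − *a*)/(*b* − *a*) × (*B* − *A*). In the example above, 53 becomes −0.2 and 47 becomes −0.8; the fall is 0.6 SD and is not flagged. With unchanged, evenly spaced norms, no 0.75 SD fall and every 1 SD fall is flagged.
2. Mark scores outside the table as out of range. Do not extrapolate, since values beyond the table have no normative basis.
3. Use the same age norm for the pre-dose benchmark and the on-treatment visits, or show that version as a sensitivity listing.

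The limit of 1 SD at two consecutive visits can stay. The cost is a few sentences in the SAP, a small programming change and slightly different flag counts; no new data are needed.

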12. CLINICAL PHARMACOKINETIC AND PHARMACODYNAMIC ANALYSES

12.1. Pharmacokinetics Population and Pharmacodynamic Population,

Please see Section 4.

12.2. Pharmacokinetic Methods

All of the pharmacokinetic analyses will be performed using the Pharmacokinetic Analysis Set.

12.2.1. Concentration Data

Blood samples will be collected prior to dosing for analysis of plasma trough concentrations of PF-00547659. Plasma concentrations at each nominal time post dose will be presented by treatment group and summarized using descriptive statistics which include n, mean, median, SD, coefficient of variation (CV), minimum and maximum. A listing of all concentrations will be provided along with scheduled and actual sampling times. A spaghetti plot of individual subject plasma-concentration against actual time post dose (separate plot for each treatment group). Mean concentrations against nominal time will be plotted for each treatment group. This plot will be presented on linear-linear and log-linear scales. These data will be analyzed for the PK population.

Further details of the Population PK methodology will be described in the separate Population Modeling and Analysis Report.

12.2.2. Handling BLQ Values

For PK concentrations, in the listings, Concentrations below the limit of quantification (BLQ) values will be reported as “<LLQ”, where LLQ will be replaced with the value for the lower limit of quantification.

For PD and biomarkers with concentrations outside the limit of quantification, in all data presentations (except listings), assayed values below the limit of quantification (BLQ) will be set to 10% less than the given assay lower limit for the specific biomarker. In addition, assayed values above the limit of quantification (ALQ) will be set to 10% more than the assay upper limit if applicable. In listings BLQ values will be reported as “<LLQ” and ULQ values will be reported as “>ULQ” where LLQ and ULQ will be replaced with the values for the lower and upper limits for qualification respectively.

No missing values will be imputed.

12.2.3. Pharmacokinetic Parameters

Please see the separate Population Modeling and Analysis Report.

12.3. Statistical Analysis of Pharmacokinetic Data

Please see the separate Population Modeling and Analysis Report.

12.4. Pharmacodynamic Methods

All of the Pharmacodynamic analyses will be performed using the Pharmacodynamic Analysis Set.

Pharmacodynamic parameters: Fecal calprotectin, hsCRP and Soluble MAdCAM will be summarized as specified below.

12.5. Statistical Analysis of Pharmacodynamic Data

Descriptive statistics (n, mean, SD, coefficient of variation, median, maximum, minimum, geometric mean, and coefficient of variation of geometric mean) for fecal calprotectin, hsCRP and soluble MAdCAM will be presented by timepoint as indicated below, treatment group and their treatment in the A7281009 study and overall. Geometric mean percent change from baseline and 90% CIs for these endpoints will also be summarized.

- hsCRP from blood samples will be summarized for the following timepoints: prior to dosing at baseline and every 4 weeks to Week 24, Week 32 and Week 72.
- Fecal calprotectin from stool samples will be summarized at the same time points as for hsCRP.
- Soluble MAdCAM in blood will be summarized for baseline and Week 16.

The following figures will also be provided for the following endpoints:

- hsCRP geometric mean over time with geometric mean SD.
- hsCRP geometric mean percent change from baseline with geometric mean SD.
- Fecal calprotectin geometric mean over time with geometric mean SD.
- Fecal calprotectin geometric mean percent change from baseline with geometric mean SD.

Fecal calprotectin, hsCRP, and soluble MAdCAM will be listed.

13. OTHER ANALYSES

Not applicable

14. INTERIM ANALYSIS

14.1. Interim Analyses

Two interim analyses (IAs) were planned to be performed for this study when 50% of subjects from the Phase 2 study (A7281009) had been enrolled in this study (A7281010), and the last subject from the Phase 2 study (A7281009) had been enrolled in this study (A7281010). In practice, two IAs occurred, one at the time of the topline report for the A7281009 study and one for an end of phase 2 meeting. The purpose of the IAs was to provide additional data on the durability of response, remission, and safety from A7281009, to facilitate the decision-making process of future studies.

14.2. Data Monitoring Committee

An external Data Monitoring Committee was placed to review the safety of subjects on an ongoing basis and to adjudicate any subjects with unexplained neurological or cardiac findings. Membership of this committee included a neurologist with expertise in PML and a cardiologist with expertise in heart failure and/or myocarditis. Work-up of suspected PML cases included a neurology consultation as well as an MRI scan, and a lumbar puncture, if clinically indicated. Given the lack of therapeutic options for subjects who have failed at least 1 conventional therapy, SHP647 with its distinct mechanism of action and known safety profile appears to have a favorable Risk-Benefit profile. The added precautions regarding PML served to increase the confidence in SHP647 for future development.

Additional cardiac monitoring was implemented in this study. Serum samples for CPK (with reflex isoenzymes), troponin I and NT-proBNP were drawn with the safety labs. Elevation of troponin I >0.05 ng/mL or CPK with MB prompted a cardiology consult. Any subject who experienced an initial on-study elevation of NTproBNP to >300 pg/mL had an echocardiogram and cardiology consult. All subjects who had an echocardiogram, in whom the NTproBNP remains >124 pg/mL at the 144 week visit, had a repeat echocardiogram and cardiology consultation ordered no later than the following visit. All cases of on-study elevation of NTproBNP to >300 pg/mL, elevation in cardiac troponin I (cTnI) or CK/MB or new ECG changes was reviewed by the DMC.

The DMC is responsible for ongoing monitoring of safety of subjects in the study according to the Charter. The recommendations made by the DMC to alter the conduct of the study or amend the protocol was forwarded to Shire for final decision. Shire will forward such decisions, which may include summaries of aggregate analyses of endpoint events and of safety data that are not endpoints, to regulatory authorities, as appropriate.

15. COMPUTER METHODS

Statistical analyses will be performed using Version 9.4 (or newer) of SAS[®] on a suitably qualified environment.

16. CHANGES TO ANALYSES SPECIFIED IN PROTOCOL

Dose escalation was removed in protocol amendment 3, SAP accommodates for subjects enrolled under prior to protocol amendment.

Gene expression profiling (mRNA) and proteins will not be analyzed. JC Virus DNA will not be analyzed.

17. DATA HANDLING CONVENTIONS

17.1. General Data Reporting Conventions

Continuous variables will be summarized using the following descriptive statistics: n, mean, median, standard deviation, minimum, maximum. Categorical and count variables will be summarized by the number of subjects (n) and the percent of subjects in each category. Percentages will be presented to a single decimal place.

17.2. Derived Efficacy Endpoints

17.2.1. Imputation Method

For analyses of binary endpoints in exploratory efficacy endpoints, the non-responder imputation method will be used for missing value imputation from drop out subjects. Subjects that have missing data which means it is not possible to determine their remission/clinical response/mucosal healing will be assigned as having no remission/no clinical response/no mucosal healing to the missing visits.

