3.3. Exploratory Objectives

- Exploratory objectives include an assessment of the durability of response with long term treatment with SHP647 based upon Clinical Remission and Clinical Response based upon the Mayo Score performed at Week 16 in Clinical Responders from study A7281009.
- Explore relationships between PK of SHP647, PD and clinical endpoints.

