9. PRIOR AND CONCOMITANT MEDICATION

Version dated 01 December 2016 of the WHO Drug Dictionary will be used to classify prior and concomitant medications by preferred term name.

Prior medication is defined as any medication with the start date prior to the date of the first dose of investigational product within A7281010.

Concomitant medication is defined as any medication with a start date prior to the date of the first dose of investigational product and continuing after the first dose of investigational product or with a start date between the dates of the first and last doses of investigational product, inclusive. Any medication with a start date after the date of the last dose of investigational product will not be considered a concomitant medication.

All the medications from A7281009 study will be imported to A7281010 study. If the medication is discontinued at end of study A7281009, it will be considered as Prior for study A7281010 whereas if medication is ongoing, then it will be considered as concomitant for study A7281010

Both prior and concomitant medication usage will be summarized by the number and percentage of subjects in each treatment group receiving each medication within each preferred term for the safety analysis set. Medications can be counted both as prior and concomitant medication. Multiple medication usage by a subject in the same category will be counted only once.

All prior and concomitant medication will be listed.

Subjects in the follow up period will be characterized by additional biologic therapy (anti-TNF (Adalimumab, Certolizumab, Certolizumab Pegol, Golimumab, Infliximab), Vedolizumab and Other Biologics (Ustekinumab)) and summarized by treatment group. Additional biological therapies will be listed.

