10. EFFICACY ANALYSES

The safety analysis set will be used for all efficacy analyses. No formal statistical analyses will be performed. Descriptive statistics will be provided for the exploratory efficacy analysis. The continuous variables will be summarized with n, mean, standard deviation, minimum, median and maximum by treatment and time point. The categorical endpoints will be summarized with frequency counts and percentages by treatment and time point. All summaries will be presented by A7281010 treatment group as defined in [Section 5](#).

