17.5. Missing Date Information for Prior or Concomitant Medications

For prior or concomitant medications, including rescue medications, incomplete (ie, partially missing) start date and/or stop date will be imputed. When the start date and the stop date are both incomplete for a subject, impute the start date first.

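### Non-responder imputation covers missing data only, so a subject who starts rescue or other active colitis treatment, stays on study and meets the score criterion counts as an SHP647 success

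*SAP*

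**What the plan says.** SAP Section 17.2.1 sets the only handling rule for the binary efficacy endpoints: "the non-responder imputation method will be used for missing value imputation from drop out subjects". Its second sentence gives the trigger: "Subjects that have missing data which means it is not possible to determine their remission/clinical response/mucosal healing will be assigned" to failure, and only at the visits that are missing. The endpoints themselves are defined by scores alone: mucosal healing in Section 10.2, and response and remission in Tables 2 to 4 of Section 10.3.1. On the population, Section 10 states: "The safety analysis set will be used for all efficacy analyses". The observed-case repeats change how missing values are treated and nothing else.

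Added medication appears elsewhere. Section 17.5 reads: "For prior or concomitant medications, including rescue medications, incomplete (ie, partially missing) start date and/or stop date will be imputed". Section 9 counts as concomitant any drug "with a start date between the dates of the first and last doses of investigational product, inclusive", as well as drugs continuing from before the first dose, and these are "summarized by the number and percentage of subjects in each treatment group receiving each medication within each preferred term". On extra biologics, Section 9 says: "Subjects in the follow up period will be characterized by additional biologic therapy". That concerns follow-up only, where the schedule shows no Mayo or SCCAI assessment.

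The exploratory objective in Section 3.3 is "an assessment of the durability of response with long term treatment with SHP647", judged on the Mayo Score at Week 16 in A7281009 clinical responders.

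**The concern.** The rule treats two kinds of treatment failure in opposite ways. A subject who flares and leaves has missing visits and is a failure. A subject who flares, receives additional active treatment, stays and improves is a success credited to SHP647. The table then describes SHP647 plus whatever was added, while the objective concerns durability under SHP647.

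This matters most for the Week 16 durability table. It also matters for the Partial Mayo and SCCAI tables, which Section 10.3.1 presents by monthly visit and the schedule carries to Week 144, so that the opportunity for added treatment accumulates. Section 14.1 says the interim durability data were meant to inform decisions on future studies, so these descriptive rates are put to use.

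The medication tables do not let a reader correct for it. They split a drug class over preferred terms and mix drugs continued from A7281009 with drugs newly started on study.

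**Working it through.** **Tracing the rule.** The places where added treatment could enter the efficacy analysis are:

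- Imputation rule (17.2.1): triggered only by missing data.
- Endpoint definitions (10.2; Tables 2 to 4): scores only.
- Analysis set (10): the whole safety set, with no exclusion.
- Sensitivity analysis (10.2, 10.3.1): observed cases, same gap.
- Medication data (9, 17.5): dated and tabulated, not linked to any endpoint.

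The SAP contains no rule for failure, exclusion, censoring or sensitivity after added treatment.

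**Can the situation arise?** In the schedule footnotes (Section 2.4), footnote s dispenses stool containers at Visits 7 and 9–17 to subjects who have had a flare, and footnote i requires a stool test in subjects who flare. Section 10.3.2 analyses dose escalation for loss of response. A flare or loss of response therefore did not by itself end participation. None of this shows that rescue treatment was compatible with staying on study.

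**Direction.** A count that keeps responders after added treatment cannot be lower than one that scores them as failures.

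**Size.** The SAP states no figure on this point to reproduce. Excess = q × s, where q is the share who start added treatment before the visit and are still on study, and s is the share of those meeting the criterion. Both are assumptions:

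| q | s = 40% | s = 60% |
|---|---|---|
| 5% | 2 points | 3 points |
| 10% | 4 points | 6 points |
| 20% | 8 points | 12 points |

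If q = 0, the excess is 0.

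**Illustration in whole subjects.** About 270 subjects (Section 2.5) split 1:1 (Section 2.2) gives 270 / 2 = 135 per starting dose. Assume 40% response under the current rule: 54/135 = 40.0%, 90% Wilson interval 33.3% to 47.1%, half-width (47.1 − 33.3) / 2 = 6.9 points. With q = 10% and s = 50%, 135 × 0.10 × 0.50 = 6.75, about 7 subjects. Scoring them as failures gives 47/135 = 34.8% (28.4% to 41.8%), a drop of 7/135 = 5.2 points.

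**Stated durability group.** The Week 16 objective concerns prior responders, whose number the SAP does not give. If half of each group were responders (assumption, about 67), the 90% Wilson half-width at 40% would be about 9.7 points. The excess is still q × s, with q and s taken among prior responders, but it is smaller relative to the interval.

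**The case against.** The strongest reply is that the answer may lie in the protocol. Permitted treatments and withdrawal rules normally belong there. If rescue means withdrawal, later visits are missing and Section 17.2.1 already makes them failures. If the added drug is prohibited, its use is a deviation reviewed under Section 6. This stands as a limit on size: the effect could be zero. It does not repair the SAP, which nowhere says so.

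The evidence that rescue is expected is also thin. Section 17.5 is the SAP's only mention, and it could be template text: Section 17.8 refers to double-blind product in an open-label study. That is fair, but Section 9 independently covers drugs started during treatment.

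Using observed scores regardless of added treatment is a legitimate treatment-policy choice in a long-term extension. That also stands, but the SAP does not state that choice.

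Efficacy is descriptive, no hypothesis is tested and the primary objective is safety. Subjects escalated from 75 mg to 225 mg have their own display group, and all medications are listed by subject (Listing 16.2.4.4).

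A reader might infer that durability is shown to be inflated, that a difference between doses or former treatments is being hidden, or that the medication data are unusable. The SAP supports none of these. It gives no rescue rate, overall or by group, no group comparison is tested, and subject-level listings exist.

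**Conclusion.** The point holds in conditional form. As written, the SAP counts any subject who starts added colitis treatment, remains on study and meets the score criterion as a responder, remitter or healed. Relative to response attributable to SHP647 without that treatment, the reported proportions can only be too high, by q × s.

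Under the assumed 5–20% and 40–60% this is 2 to 12 points. It is zero if the protocol requires withdrawal at rescue or if nobody receives it. The range rests wholly on assumed inputs, and the 135-per-group illustration is not the denominator of the stated durability objective.

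Because efficacy is descriptive and durability exploratory, this should be corrected before database release but does not undermine the study's primary purpose.

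**What to change.** 1. In Section 17.2.1, define a flag for the first start or restart after Day 1 of rescue or other active colitis treatment. Include dose increases if dose changes are recorded. Take the drug list from the protocol and have it reviewed before database release.
2. In the non-responder imputation tables, count flagged subjects as non-response, non-remission and not healed at visits after that start.
3. Show the current rule (observed score used regardless of added treatment, missing counted as failure) as the treatment-policy sensitivity version. Do not give that label to the observed-case tables, which leave out subjects with missing outcomes.
4. Report the number flagged by visit and treatment group. In Section 9, summarise on-study starts of colitis medication by class.
5. Note that the A7281009 Week 12 status is carried over unchanged (Section 17.2.2), so the rule applies only to visits after Day 1. Footnote this where Baseline and Week 16 stand side by side.
6. State how imputed dates enter the flag. Section 17.5.1 sets a start with a missing day in the month of first dose to the first-dose date, which a rule based on starts after Day 1 would miss.

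If the protocol already requires withdrawal at rescue, a sentence in Section 17.2.1 saying so settles the matter for rescue treatment.

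The cost is SAP wording, one variable derived from medication data already collected, and the drug-list review. Reported rates may be somewhat lower. This is an analysis rule only; no clinical rule on rescue use is proposed.
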